2.3.1.2.2 Freedom from Major Adverse Events (MAE) at 30 Days Post Procedure

A composite of cardiovascular mortality, new onset renal failure, endocarditis requiring surgery, and non-elective cardiovascular surgery for TriClip™ device-related adverse event post-index procedure will be

Statistical Analysis Plan

used as a secondary measure of safety. The analysis of this secondary endpoint is a one-group test against a performance goal (PG) for the proportion of subjects in the Attempted Procedure population free from the composite of this secondary endpoint of MAE at 30-day post procedure.

The null and alternative hypotheses are stated as:

$$H_0: P_{30D}(MAE) \leq 90\%$$

$$H_1: P_{30D}(MAE) > 90\%$$

where $P_{30D}(MAE)$ is the probability of freedom from any MAE at 30-day post procedure. [REDACTED]

[REDACTED]

[REDACTED] E

The null hypothesis will be rejected at a one-sided 2.5% level of significance.

[REDACTED]

2.3.1.2.3 Change in Quality of Life (Kansas City Cardiomyopathy Questionnaire, KCCQ) at 12 Months over Baseline

Improvement in quality of life as measured by the KCCQ test at 12 months from baseline will be a secondary effectiveness endpoint in the comparison of the Device group to the Control group.

The null and alternative hypotheses are stated as:

$$H_0: \mu_{D, \Delta KCCQ} - \mu_{C, \Delta KCCQ} = 0$$

$$H_1: \mu_{D, \Delta KCCQ} - \mu_{C, \Delta KCCQ} \neq 0$$

where $\mu_{D, \Delta KCCQ}$ and $\mu_{C, \Delta KCCQ}$ represent the mean change in quality of life score between 12 months and baseline in the Device and Control groups respectively.

The analysis will be performed in subjects with paired KCCQ data at baseline and 12 months. Subjects who experience an adjudicated heart failure related cardiovascular death or receive the Tricuspid Valve surgery prior to completing the 12 months follow-up will also be included in the analysis. Their KCCQ score at 12 months will be imputed as 0 points.

ANCOVA will be used to compare the mean changes in KCCQ score between 12 months and baseline in the two groups, while adjusting for the baseline KCCQ score. The null hypothesis will be rejected a two-sided 5% level of significance.

Statistical Analysis Plan

2.3.1.2.4 Change in 6MWT (Six Minute Walk Test) Distance at 12 Months over Baseline
Improvement in the 6MWT distance at 12 months from baseline is an important secondary effectiveness endpoint in the comparison of the Device group to the Control group.

The null and alternative hypotheses are stated as:

$$H_0: \mu_{D, \Delta 6MWD} - \mu_{C, \Delta 6MWD} = 0$$

$$H_1: \mu_{D, \Delta 6MWD} - \mu_{C, \Delta 6MWD} \neq 0$$

where $\mu_{D, \Delta 6MWD}$ and $\mu_{C, \Delta 6MWD}$ represent the mean change in 6MWT distance between 12 months and baseline in the Device and Control groups respectively.

The analysis will be performed in subjects with paired 6MWT data at baseline and 12 months. [REDACTED]

[REDACTED]
[REDACTED]
[REDACTED]
[REDACTED]
[REDACTED]
[REDACTED]
[REDACTED] The null hypothesis will be rejected at a two-sided 5% level of significance.

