### **4.2 Measures Taken to Avoid and Minimize Bias**

Due to the nature of the treatment in the two randomized groups, the subject, some site personnel and some Sponsor personnel will be aware of treatment assignment. The following steps will be taken to minimize bias in the conduct of the trial and analyses of clinical data.

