**TRILUMINATE Pivotal CIP**  
(Version F)

- Incidence of ascites at 12 months, and annually through 24, 36, 48, and 60 months
- Incidence of IV diuretic administration (including outpatient clinics) at 12 months, and annually through 24, 36, 48, and 60 months
- Change in KCCQ score from baseline through 30 days, 6 months, 12 months and annually through 24, 36, 48, and 60 months
- SF-36 QoL scores at baseline, 30 days, 12 months and 24 months (and change from baseline to follow-up)
- Change in NYHA Functional Class (III/IV to I/II) from baseline through 30 days, 6 months, 12 months and annually through 24, 36, 48, and 60 months
- Change in 6MWT from baseline through 30 days, 6 months, 12 months and annually through 24, 36, 48, and 60 months
- Change in BNP/NT-proBNP from baseline through 30 days, 6 months, 12 months, and annually through 24, 36, 48, and 60 months
- Change in gamma-GGT from baseline through 30 days, 6 months, 12 months, and annually through 24, 36, 48, and 60 months
- Change in patient weight from baseline through 30 days, 6 months, 12 months and annually through 24, 36, 48, and 60 months
- Change in kidney function (assessed using eGFR) from baseline through 30 days, 6 months, 12 months and annually through 24, 36, 48, and 60 months
- Change in liver function (assessed using the MELD score) from baseline through 30 days, 6 months, 12 months and annually through 24, 36, 48, and 60 months
- Echocardiographic endpoints assessed from baseline through 30 days, 6 months, 12 months and annually through 24, 36, 48, and 60 months post procedure, as follows:
  - TR severity grade
  - Tricuspid valve annulus diameter
  - Effective Regurgitant Orifice Area (EROA)
  - Regurgitant Volume
  - Vena Contracta Width
  - Right Ventricular End Diastolic Dimension (RVEDD)
  - Right Ventricular Fractional Area Change
  - Left Ventricular End Diastolic Volume (LVEDV)
  - Left Ventricular End Systolic Volume (LVESV)
  - Tricuspid Annular Plane Systolic Excursion (TAPSE)
  - Cardiac Output
  - Forward Stroke Volume (Left Ventricle)
  - Inferior Vena Cava Dimension

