2.3.1.2 Randomized Cohort – Secondary Endpoints

The following six secondary endpoints will be used as secondary measures of safety and effectiveness for the TriClip™ system. The secondary endpoints will be tested at a two-sided 5% level of significance unless otherwise specified. The primary analysis population of the secondary endpoints will be the ITT population. Additional analyses may be performed on the PP and AT populations.

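### The primary analysis of 12-month KCCQ change is complete-case for living, non-operated subjects and leaves their 30-day and 6-month scores unused

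*SAP*

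**What the plan says.** SAP 2.3.1.2 sets the population: "The primary analysis population of the secondary endpoints will be the ITT population". For the 12-month KCCQ change, SAP 2.3.1.2.3 then restricts the data: "The analysis will be performed in subjects with paired KCCQ data at baseline and 12 months". Two groups are added: "Subjects who experience an adjudicated heart failure related cardiovascular death or receive the Tricuspid Valve surgery prior to completing the 12 months follow-up". For both, "Their KCCQ score at 12 months will be imputed as 0 points". The model is an ANCOVA with baseline KCCQ as the only stated covariate: "ANCOVA will be used to compare the mean changes in KCCQ score between 12 months and baseline in the two groups".

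KCCQ is collected more often than this model uses. Protocol 5.1.3 lists "Change in KCCQ score from baseline through 30 days, 6 months, 12 months" among the descriptive endpoints, and the schedule in Protocol 7.15 (Table 1) confirms the 30-day and 6-month questionnaires.

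Four other provisions bear on the point:

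- Protocol 4.2 states that "the subject, some site personnel and some Sponsor personnel will be aware of treatment assignment". Only the staff who administer the questionnaire are blinded (Protocol 4.2.3).
- Protocol 7.11 allows Controls to receive TriClip only once the 12-month visit is complete.
- SAP 2.3 removes KCCQ recorded after a first adjudicated COVID-19 hospitalization from the primary analysis.
- SAP 2.11.1 places this endpoint second of six in the fixed testing sequence for labeling claims.

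The text of SAP 2.9 and Protocol 9.7 on missing data, and part of SAP 2.12 on sensitivity analyses, is blacked out.

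**The concern.** The readable text defines the primary analysis, and that analysis makes no use of what is known about a subject between baseline and month 12. A subject who was much better or much worse at 6 months and then missed month 12 is treated as if baseline alone described them. Subjects know their assignment, and Controls need the 12-month visit to become eligible for the device, so attendance may well depend on how a subject feels.

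Because the endpoint is second in a fixed sequence, bias against the device could lose this claim and block the four tests below it. Bias towards the device could create a labeling claim and open those tests.

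**Working it through.** **1. The plan's own figure.** SAP 2.4.1.2.3 gives power above 90% with 350 randomized subjects at two-sided 5%. The effect, SD and attrition behind it are blacked out, so it cannot be reproduced. It can be inverted to give a yardstick. The difference detectable with 90% power is (1.960 + 1.282) × SD × √(2/175). The only SD of KCCQ change in the documents is 16.74 (Protocol 2.1.4; single-arm, 30 days), which gives 5.8 points. SDs of 20, 25 and 30, taken as assumptions, give 6.9, 8.7 and 10.4.

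**2. Who enters the stated analysis.**

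| Subject | Treatment in SAP 2.3.1.2.3 |
|---|---|
| Baseline and 12-month KCCQ present | Included as observed |
| HF-related cardiovascular death, or tricuspid surgery, before completing 12 months | Included, 12-month score 0 |
| Alive, no surgery, no usable 12-month KCCQ | Dropped, even with 30-day and 6-month scores |
| Death not adjudicated as HF-related cardiovascular | Not provided for |

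**3. When this is unbiased.** Let e be the 12-month score after removing the effects of arm and baseline, so e averages 0 in each arm. With a fraction m missing, (1 − m) × (mean e if observed) + m × (mean e if missing) = 0. Hence:

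mean e if observed = −[m/(1 − m)] × (mean e if missing).

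The bias is the Device value minus the Control value. If missingness depends only on arm and baseline, mean e among the missing is 0 and there is no bias, whatever the two rates are. A simulation agrees: with 25% missing in Control and 5% in Device, completely at random or depending on baseline only, the bias was about 0 (Monte Carlo error about 0.1 point).

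**4. Missingness that depends on the 6-month score.** All inputs here are assumptions: 175 per arm, no true effect, residual SD about 16.7, residual correlation 0.7 between months 6 and 12, Device 8% missing. Lower 6-month scores raise the odds of missing month 12 by the odds ratio shown per SD.

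SE = 16.74 × √(1/161 + 1/157.5) = 1.88, from 175 × 0.92 = 161 and 175 × 0.90 = 157.5. It is 1.90 at 15% missing; 1.88 is used throughout.

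Two-sided error = Φ(−1.96 − b/SE) + Φ(−1.96 + b/SE), where b is the absolute bias.

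| Control missing | Odds ratio | Bias, dependence in Control only | Error | Bias, same dependence in both arms | Error |
|---|---|---|---|---|---|
| 10% | 2.7 | 1.08 | 8.9% | 0.20 | 5.1% |
| 15% | 2.7 | 1.57 | 13.3% | 0.69 | 6.6% |
| 15% | 4.5 | 2.07 | 19.6% | 0.88 | 7.6% |

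First row worked: 1.08/1.88 = 0.574, and Φ(−2.534) + Φ(−1.386) = 0.6% + 8.3% = 8.9%.

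Step 3 shows what the Control-only column requires. A bias of 1.08 at 10% missing means that missing Controls score 1.08 × 0.90/0.10 = 9.7 points away from their baseline-predicted value. A bias of 2.07 at 15% means 2.07 × 0.85/0.15 = 11.7 points. Missing Device subjects are exactly on prediction in both cases.

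In these settings, imputation from the 6-month score left a bias below 0.1 point.

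**5. A milder setting.** The SDs in Protocol 2.1.4 imply a baseline correlation of (21.85² + 22.24² − 16.74²)/(2 × 21.85 × 22.24) = 0.71. The assumptions were a correlation of 0.75 among later visits, the same dependence in both arms (odds multiplied by e per SD lower), 5% missing in Device and 10-25% in Control. The bias was 0.3 to 0.9 points, and the error was 5.5% at 15%/5% and 8.0% at 25%/5%. Using the 30-day and 6-month scores again removed the bias.

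**6. Missingness that depends on the unseen 12-month score.** In the setting of step 5, paired-data bias was 0.5 to 1.9 points and 0.3 to 1.4 after using the intermediate visits. At 25%/5% it fell from 1.87 to 1.35, a reduction of (1.87 − 1.35)/1.87 = 28%. With the inputs of step 4 the reduction was about 35-50%. The intermediate visits help here but do not solve the problem.

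The simulations in steps 4 to 6 omit the zero-scored subjects. These would widen the SE, so the error rates are for orientation.

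**The case against.** The strongest reply is that the size rests entirely on assumptions, and on a strong one at the upper end. The 9-20% error appears only if Control missingness depends on outcome while Device missingness does not. With shared dependence it is 5-8%. Protocol 4.2.7 also provides retention measures, including in-home visits if necessary, and the blacked-out sections may already contain an imputation or repeated-measures analysis. All of this stands and limits the size. It does not change the primary rule that can be read in SAP 2.3.1.2.3.

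A reader might infer four stronger points that the documents do not support:

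- **That unequal missingness by itself biases the comparison.** Step 3 shows that it does not.
- **That Controls who feel no better will skip month 12.** Protocol 7.11 gives them a reason to attend, since the visit must be completed before they can receive TriClip. If worse-off Controls did go missing, the bias would work against the device: at 1.08 points, false rejection in the device's favor is 0.6%, below the nominal 2.5%. If better-off Controls go missing, it is 8.3%. The crossover rule makes that second route conceivable, but nothing in the documents establishes either.
- **That the analysis is not ITT.** The ITT definition is blacked out in both documents, so this cannot be shown.
- **That only paired subjects are analyzed.** The two zero-scored groups are added.

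**Conclusion.** The concern holds as a weakness of the stated primary analysis. For living, non-operated subjects it is complete-case, and it needs missingness to be unrelated to outcome given baseline and arm. Scores already scheduled would allow a weaker assumption.

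Under the assumed inputs the bias is about 0.2 to 0.9 points with shared dependence and about 1 to 2 points with dependence in Control only. Against the 5.8-point yardstick in step 1, that is 3% (0.20/5.8) to 36% (2.07/5.8). The direction is uncertain. The missingness rates, the strength of dependence and the correlation between later visits are assumptions, because the documents give none of them. This is a change that should be made; it does not show that the KCCQ result will be wrong.

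**What to change.** Amend SAP 2.3.1.2.3 as follows:

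- For living, non-operated subjects without a usable 12-month KCCQ, use multiple imputation by arm from baseline, 30-day and 6-month KCCQ, then the stated ANCOVA. A repeated-measures model with those visits is an alternative.
- Keep the zero-score rule for the two groups that have it.
- State how deaths not adjudicated as HF-related cardiovascular are handled, and how KCCQ censored after a COVID-19 hospitalization is handled. Scores recorded before that hospitalization can still inform an imputation.
- Keep the paired-data ANCOVA as a sensitivity analysis.
- Add a delta-adjusted missing-not-at-random analysis, because step 6 shows that the intermediate visits remove only part of that bias.

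If SAP 2.9 already specifies this, reconcile the two sections so that one primary rule is stated.

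The cost is SAP wording and programming; no new data are needed. The primary result would then rest on missingness being at random given the observed visits, which is weaker than the present assumption but still cannot be tested.

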2.3.1.2.5 Recurrent HF Hospitalizations at 24 Months

Treatment with the TriClip™ device is expected to reduce the risk of recurrent HF hospitalizations. The null and alternative hypotheses are stated as:

$$H_0: HR(24M) > 1$$

$$H_1: HR(24M) \leq 1$$

where $HR(24M)$ is the hazard ratio of recurrent HF hospitalization between the Device and Control groups. Hospitalizations that are adjudicated by the CEC as related to heart failure using the pre-specified Clinical Investigational Plan definition will be included as events in the analysis.

[REDACTED]
[REDACTED]
[REDACTED]
[REDACTED]
[REDACTED]
[REDACTED]
[REDACTED] Beneficial treatment effect is established if the upper one-sided 95% confidence limit of the hazard ratio is smaller than 1.

Statistical Analysis Plan

2.3.1.2.6 Freedom from All-Cause Mortality, Tricuspid Valve Surgery, and Tricuspid Valve Intervention at 24 Months

The difference in risk of all-cause mortality or Tricuspid Valve surgery or intervention at 24 months between the Device and Control groups is a secondary measure of safety. The null and alternative hypothesis are stated as:

H₀: Survival curves of the two groups through 24 months are the same.

H₁: Survival curves of the two groups through 24 months are different.

[REDACTED]
[REDACTED] The null hypothesis will be rejected with a two-sided 5% level of significance.

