2.3.2.2.4 Recurrent HF Hospitalizations at 12 Months

The null and alternative hypotheses are stated as:

$$H_0: \lambda_{12M}(\text{PRE}) \leq \lambda_{12M}(\text{POST}) \text{ vs.}$$

$$H_1: \lambda_{12M}(\text{PRE}) > \lambda_{12M}(\text{POST})$$

where $\lambda_{12M}(\text{PRE})$ and $\lambda_{12M}(\text{POST})$ represent the annualized event rates for recurrent HF hospitalizations within 12 months prior to (PRE) and on or after (POST) study enrollment.

[REDACTED]

[REDACTED]

The null hypothesis will be rejected at a one-sided 2.5% level of significance.

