2.4.1.2.5 Recurrent HF Hospitalizations at 24 Months

The power calculations for the recurrent HF hospitalizations at 24 months is based on the following assumptions:

- █ [Redacted]
- █ [Redacted]
- █ [Redacted]
- █ [Redacted]
- █ [Redacted]
- █ [Redacted]
- █ [Redacted]
- █ [Redacted]
- █ [Redacted]
- █ [Redacted]
- █ [Redacted]
- █ [Redacted]
- █ [Redacted]
- █ [Redacted]
- █ [Redacted]
- █ [Redacted]
- █ [Redacted]
- █ [Redacted]
- █ [Redacted]
- █ [Redacted]

Statistical Analysis Plan

Ten thousand (10,000) simulations were performed to calculate the sample size and power for this secondary endpoint. Based on the assumptions, with 450 randomized subjects, the power is approximately 80% to reject the null hypothesis at a one-sided 5% level of significance.

2.4.1.2.6 Freedom from All-Cause Mortality, Tricuspid Valve Surgery, and Tricuspid Valve Intervention at 24 Months

The power calculations for all-cause mortality or tricuspid valve surgery or intervention at 24 months is based on the following assumptions:

- [REDACTED]
- [REDACTED]
- [REDACTED]
- [REDACTED]
- [REDACTED]
- [REDACTED]
- [REDACTED]

Ten thousand (10,000) simulations were performed to calculate the sample size and power for this secondary endpoint. Based on the assumptions, with 450 randomized subjects, the power is approximately 80% to reject the null hypothesis at a two-sided 5% level of significance.

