2.4.2.2.4 Recurrent HF Hospitalizations at 12 Months

The power calculations for recurrent HF hospitalizations at 12 months for the Single-Arm Cohort is based on the following assumptions:

■ [REDACTED]

[REDACTED]

■ [REDACTED]

Statistical Analysis Plan

[REDACTED]

Ten thousand (10,000) simulations were performed to calculate the sample size and power for this secondary endpoint. Based on the assumptions, with approximately 100 subjects, the power is approximately 83% to reject the null hypothesis at a one-sided 2.5% level of significance.

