2.11 Multiplicity Issues

Since the analysis population for the Randomized Cohort and Single-Arm Cohort are mutually exclusive, the primary and secondary endpoints for the Randomized Cohort and Single-Arm Cohort will be evaluated separately and need no multiplicity adjustment. Within each cohort, sequential testing will be performed for the pre-specified endpoints. Therefore, the overall type I error is under control.

Statistical Analysis Plan

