2.11.1 Multiplicity – Randomized Cohort

The secondary endpoints for the Randomized Cohort will be evaluated for labeling claims if the primary endpoint is met. The secondary endpoints for the Randomized Cohort will be tested sequentially in the following order:

- Freedom from major adverse events (MAE) occurring after procedure attempt (femoral vein puncture) at 30 days.
- Change in KCCQ at 12 months over baseline (superiority of Device vs. Control)
- TR Reduction to moderate or less at 30 days post procedure (superiority of Device vs. Control)
- Change in 6MWT at 12 months over baseline (superiority of Device vs. Control)
- Recurrent HF hospitalizations at 24 months (superiority of Device vs. Control)
- Freedom from all-cause mortality, tricuspid valve surgery, and tricuspid valve intervention at 24 months (superiority of Device vs. Control)

The two secondary endpoints assessed at 24 months (recurrent HF hospitalizations and freedom from all-cause mortality, tricuspid valve surgery and tricuspid valve intervention) will be evaluated when all randomized subjects complete 24-month follow-up for additional labeling claims.

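### Does testing recurrent HF hospitalization at one-sided 5%, when the other randomized tests allow 2.5% in the device's favor, call for a change?

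*SAP*

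**What the plan says.** SAP 2.3.1.2 sets the default for the randomized secondary endpoints: "The secondary endpoints will be tested at a two-sided 5% level of significance unless otherwise specified". SAP 2.3.1.2.5 then specifies otherwise for recurrent HF hospitalization. The hypotheses are one-directional, and the decision rule is: "Beneficial treatment effect is established if the upper one-sided 95% confidence limit of the hazard ratio is smaller than 1". SAP 2.4.1.2.5 powers the test at the same level: "with 450 randomized subjects, the power is approximately 80% to reject the null hypothesis at a one-sided 5% level of significance".

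SAP 2.11.1 places this test fifth among six secondaries, describes it as a superiority comparison of Device with Control, and ties both 24-month tests to further labeling claims. On error control, SAP 2.11 says: "Within each cohort, sequential testing will be performed for the pre-specified endpoints. Therefore, the overall type I error is under control". Neither 2.11 nor 2.11.1 gives a level for any test; the levels are in the endpoint sections.

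In the Single-arm cohort, the recurrent HF hospitalization endpoint is a comparison of rates before and after enrollment. SAP 2.3.2.2.4 says of it: "The null hypothesis will be rejected at a one-sided 2.5% level of significance". Its power statement in 2.4.2.2.4 agrees: "with approximately 100 subjects, the power is approximately 83% to reject the null hypothesis at a one-sided 2.5% level of significance".

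**The concern.** One test in the randomized sequence is easier to pass than its neighbors, and it is one that can support a labeling claim. A hazard ratio whose two-sided 95% confidence interval includes 1 could be declared a superiority finding here. Evidence of the same strength would fail at each of the other two-arm comparisons.

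The contrast with the rest of the SAP sharpens the question. Wherever else it runs a one-sided test (30-day MAE in the randomized cohort, and the Single-arm endpoints), it uses 2.5%. The same clinical outcome therefore meets a stricter level in the uncontrolled cohort than in the randomized comparison. The visible text does not explain the difference.

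Three things would be at stake: how strong the evidence behind one claim is, whether the sequence controls type I error as the SAP says, and how much of the stated 80% power comes from the looser level.

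**Working it through.** **1. Levels across the sequence.**

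| Step | Test (SAP section) | Stated level | Largest error in the device's favor |
|---|---|---|---|
| Gate | Primary composite (2.3.1.1) | two-sided 5% | 2.5% |
| 1 | 30-day MAE against the goal (2.3.1.2.2) | one-sided 2.5% | 2.5% |
| 2 | KCCQ change (2.3.1.2.3) | two-sided 5% | 2.5% |
| 3 | TR at 30 days (2.3.1.2.1) | two-sided 5% | 2.5% |
| 4 | 6MWT change (2.3.1.2.4) | two-sided 5% | 2.5% |
| 5 | Recurrent HF hospitalization (2.3.1.2.5) | one-sided 5% | 5% |
| 6 | 24-month death, surgery or intervention (2.3.1.2.6) | two-sided 5% | 2.5% |

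Step 5 is the only exception.

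**2. What the rule admits.** An upper one-sided 95% limit below 1 means z > 1.645, so two-sided p < 0.10. The other two-arm tests need z > 1.960. The extra acceptance region is z from 1.645 to 1.960. Its probability at HR = 1 is 0.050 − 0.025 = 0.025.

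**3. Familywise error.** In a fixed sequence, a false rejection anywhere requires that the first true null in the order be rejected. That test has size 5% or less, whichever step it is. So the probability of any false rejection is at most 5%. This covers step 6 too: if the step 5 null is true, step 6 is reached only by first rejecting step 5 (probability at most 5%); if it is false, step 6 has its own 5%. The SAP 2.11 statement holds at the 5% level.

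The bound on a false claim of benefit at step 5 is 5% instead of 2.5%. It is approached only if HR = 1 and the earlier steps are nearly certain to pass. I give no unconditional rate. Multiplying the planned powers of the earlier steps by an error rate at HR = 1 would be incoherent, because HF hospitalization is itself a component of the primary endpoint.

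**4. Power.** The assumptions behind the simulation are redacted, so the stated 80% can be neither reproduced nor refuted. Under a normal approximation it implies a drift of

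z(0.95) + z(0.80) = 1.645 + 0.842 = 2.486 (unrounded components).

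- Power at one-sided 2.5% with 450 subjects: Φ(2.486 − 1.960) = 0.701. If the approximate 80% means 78% or 82%, the drift is 2.417 or 2.560 and the power is 0.676 or 0.726.
- Observed effect needed to pass, as a share of the planned log hazard ratio: 1.645/2.486 = 0.66 now, 1.960/2.486 = 0.79 at the stricter level.
- Subjects needed to keep 80%: 450 × [(1.960 + 0.842)/2.486]² ≈ 571.
- Protocol 6.8 lets enrollment follow the sample size re-estimation. At 500 subjects: Φ(2.486 × √(500/450) − 1.960) ≈ 0.75. At 550: ≈ 0.78.

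**5. Effect on the last test.** Take step 6 at its stated 80% power. The chance of passing both 24-month tests is 0.80 × 0.80 = 0.640 now and 0.701 × 0.80 = 0.561 at the stricter level if they are independent. At an assumed correlation of 0.5 the figures are 0.687 and 0.616.

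**6. Hypothesis wording.** SAP 2.3.1.2.5 puts HR = 1 in the alternative. The decision rule requires the limit to lie strictly below 1, so this slip changes no result.

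**The case for a change.** The strongest case for a change is that prespecifying a level makes it transparent without making the evidence equal to that behind the other claims. About 10 of the 80 power points come from the looser level (0.80 − 0.701). The SAP's own habit for one-sided tests is 2.5%. Alignment would need only wording and one rerun of an existing simulation, with no added patients if the lower power is accepted. A rationale hidden by redaction would explain the level but would not alter it.

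Much of this stands. The directional standard is looser here, and a reader who assumes a uniform two-sided 5% would be wrong about this one test. What does not stand is the step from there to a defect. No rule in either document requires a uniform 2.5% in the device's favor; the default expressly allows exceptions, and this one is stated openly in both the analysis and power sections. SAP 2.11 is not silent on this test in particular, since it gives no level for any test. The Single-arm comparison is a before-and-after contrast in a separate cohort with its own sequence, so it sets no precedent.

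The lack of a visible reason also carries little weight. Text just before the success rule, the power assumptions for this test, Protocol 9.3.1.2 and Protocol 9.6 are all redacted.

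**Conclusion.** No change is needed. The observation is accurate: a superiority claim on this endpoint could be made at a two-sided p between 0.05 and 0.10. But it describes a choice, consistently stated and matched by its power calculation, and familywise error remains at or below 5%.

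The alternative is a trade. It would halve the bound on a false benefit claim for one late secondary endpoint. In return, an endpoint that Protocol 5.1.2 lists as powered would fall to about 70% power with 450 subjects, and the final 24-month test would be reached less often. Keeping 80% would mean about 121 more subjects (571 − 450). Competent statisticians could settle this either way.

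The reach is narrow. Trial success rests on the primary endpoint alone (SAP 2.7, Protocol 9.10), and this test opens only after that and four secondaries succeed. Anyone weighing the claim can read the level in SAP 2.3.1.2.5 and judge the result accordingly.

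The conclusion assumes that each test holds its nominal size, including the primary after a sample size re-estimation whose rules are redacted. The power figures are normal-approximation back-calculations from a rounded 80%.
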